**Noninvasive Ventilation for Preterm Neonates With
Respiratory Distress Syndrome: a Multi-center Randomized
Controlled Trial**

(NCT03099694)

13 July 2017

Solid PDF/A Express
<http://www.SolidDocuments.com/>

STUDY PROTOCOL

Noninvasive high-frequency oscillatory ventilation versus nasal continuous positive airway pressure in preterm infants with respiratory distress syndrome: Study protocol for a multi-center, prospective, randomized, controlled trial. For the Noninvasive High-Frequency Oscillatory Ventilation Study Group (NHFOV Study Group*).

Abstract

Background: Invasive mechanical ventilation is associated with development of adverse pulmonary and non-pulmonary outcomes in very low birth weight infants. Various modes of non-invasive respiratory support are being increasingly used to decrease the incidence of bronchopulmonary dysplasia (BPD). The aim of this trial is to compare the effect of noninvasive high-frequency oscillatory ventilation (NHFOV) and nasal continuous positive airway pressure (NCPAP) in preterm infants with respiratory distress syndrome (RDS) as a primary noninvasive ventilation support mode.

Methods/Design: In this multicenter, randomized, controlled trial, 300 preterm infants born at gestational age (GA) less than 34 weeks with a diagnosis of RDS will be randomized to NHFOV or NCPAP as a primary mode of noninvasive respiratory support. Study will be conducted in 18 tertiary neonatal intensive care units in China. The primary outcome is the need for invasive mechanical ventilation (IMV) during the first 7 days after enrollment in preterm infants randomized to the two groups. The

prespecified secondary outcomes include days of hospitalization, days on noninvasive respiratory support, days on IMV, days on supplemental oxygen, mortality, need for surfactant, severe retinopathy of prematurity(ROP) requiring laser or surgery, patent ductus arteriosus needing ligation, bronchopulmonary dysplasia(BPD), occurrence of abdominal distention, air leaksyndromes, intraventricular hemorrhage (IVH \geq grade 3), necrotizing enterocolitis (NEC \geq II stage) and nasal trauma. Other secondary outcomes include Bayley Scales of Infant Development at 18-24 months of corrected age.

Trial registration: ClinicalTrials.gov Identifier: NCT03099694.

Key words: Noninvasive high-frequency oscillatory ventilation; nasal continuous positive airway pressure; respiratory distress syndrome; preterm infants; surfactant; invasive mechanical ventilation

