The primary outcome of this trial will be to determine the need for IMV in the first 7 days of life in preterm infants randomized to the two groups. Secondary outcomes include days of hospitalization, days on noninvasive ventilation, days on supplemental oxygen, pre-discharge mortality, surfactant doses, incidence of stage III ROP and BPD, occurrences of abdominal distention, air leaks, IVH \geq grade 3 and NEC. Secondary outcomes also include Bayley Scales of Infant Development at 18-24 months of corrected age. BPD will be defined according to the National Institutes of Health consensus definition as mild, moderate and severe BPD [12], IVH classification according to Papile et al [13] and for NEC, Bell staging will be used [14].

Data collection

Patient demographic data include: sex, birth weight, gestational age, Apgar scores, mode of

delivery, prenatal corticosteroid use, premature rupture of the membrane, RDS Silverman score and critical risk index for babies-II (CRIB-II) score. More details see in the appendix Clinical data :Including the need for IMV, days of hospitalization, days on noninvasive respiratory support, days on supplemental oxygen, mortality, the need for surfactant, occurrences of abdominal distention, air leaks, IVH \geq grade and NEC \geq stage II. More details see in the appendix Follow-up data: The incidence of BPD and ROP at a post-menstrual age of 36 weeks or at discharge, and Bayley Scales of Infant Development at 18-24 months of corrected age.

Sample size calculation

It is difficult to calculate a sample size for such a study, since it is the first to investigate NHFOV vs CPAP in primary support phase in preterm infants with RDS. There is only one preliminary study available about the primary outcome “need for IMV”. This pilot study conducted by Zhu et al provides data about the primary outcome “need for IMV”. This trial showed the need for IMV was significantly lower in the NHFOV compared with the NCPAP group (24.3% vs. 56.4%, $P < 0.01$). Considering an α -error of 0.05 and a power of 90%, 150 neonates should be enrolled in each arm (with a 1:1 design) to detect the same difference.

Statistical methods

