Data will be analyzed using SPSS version 19 software. The statistical analyses include Student's t-test for continuous data and compared proportions using Chi-squared test, and Fisher's exact test for categorical data. Predefined four subgroups are 26^{0/7}-27^{6/7} weeks, 28^{0/7}-29^{6/7} weeks, 30^{0/7}-31^{6/7} weeks and 32^{0/7}-33^{6/7} weeks, and subgroup analyses will be conducted for the primary outcome in the preterm infants. To further evaluate the effect of NHFOV on intubation within

subgroup, the test of treatment-by-gestational age subgroup interaction will also be done using the paired binary logistic regression. For the preterm infants lost to follow-up, the missing values of the primary and secondary outcomes are replaced using multiple imputation. A P -value < 0.05 will be regarded as statistically significant.

Data Safety Monitoring Board (DSMB): [name], Professor of Pediatrics, Oklahoma University Medical Center, Oklahoma, [name], Professor of Pediatrics, Medical College of Georgia, Georgia Health Sciences University, Augusta, Georgia, and [name], MD., MPH (Biostatistics and Epidemiology) Assistant Professor of Pediatrics, Keck School of Medicine of the University of Southern California, Los Angeles, California will serve as DSMB members. [name] will also serve as consultant for statistical analysis.

Registration number

The trial has been approved by the centralized ethics committee (The Ethics Committee of Daping Hospital, Research Institute of Surgery, Third Military Medical University) and registered at <http://www.clinicaltrials.gov>(ID: NCT03099694).

Discussion

In the past decades, several clinical trials have compared the effects between NHFOV and NCPAP in neonates as a rescue mode or during weaning from IMV. These trials demonstrated that NHFOV applied with nasopharyngeal tube are more beneficial than NCPAP in reducing CO₂ levels [16-19]. Recently, two retrospective case series also reported NHFOV could be applied in preterm infants as a rescue treatment after the

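### The sample size of 150 per arm does not follow from its stated inputs, which require about 47 to 54 per arm

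*Combined protocol and SAP*

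**What the plan says.** The Sample size calculation section relies on a single pilot study for the primary outcome. It reports that the need for IMV was lower with "NHFOV compared with the NCPAP group (24.3% vs. 56.4" percent. It then sets an alpha "error of 0.05 and a power of 90" percent and concludes that "150 neonates should be enrolled in each arm (with a 1:1 design) to detect the same difference".

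The Abstract gives the matching total of "300 preterm infants born at gestational age (GA) less than 34 weeks", so 150 is not a misprint confined to one section. The primary outcome is binary: "need for IMV in the first 7 days of life in preterm infants randomized to the two groups".

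Statistical methods names the tests ("compared proportions using Chi-squared test, and Fisher's exact test for categorical data"), gives a single 0.05 threshold for significance, and deals with loss to follow-up by analysis: "the missing values of the primary and secondary outcomes are replaced using multiple imputation". Neither section mentions enrolment inflation for dropout, a design effect, an interim analysis, an alpha split or a power requirement within subgroups. The section does not say whether alpha is one-sided or two-sided.

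**The concern.** All the inputs to a two-proportion sample size are given, so the result can be checked, and a difference of 32 points between two mid-range proportions needs far fewer than 150 per arm. The text says that 150 is for the pilot's own difference, which rules out reading it as a sample size chosen for a smaller effect.

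This paragraph is the only justification for how many preterm infants are enrolled. Read literally, it tells an ethics committee that 300 infants are needed for a question that about 94 to 108 would answer at the stated power. It also names the wrong design effect: a reader would take 32 points as the difference the trial was built to find, when it has good power for a difference little more than half that size.

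**Working it through.** **Inputs.** From Sample size calculation: p1 = 0.564 (NCPAP), p2 = 0.243 (NHFOV), alpha 0.05, power 0.90, allocation 1:1. Sidedness is not stated. I take two-sided (z = 1.960) and check one-sided below. For 90% power, z = 1.2816.

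**Quantities used throughout**

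- d = 0.564 − 0.243 = 0.321, d² = 0.10304
- mean proportion = (0.564 + 0.243)/2 = 0.4035
- A = √(2 × 0.4035 × 0.5965) = √0.48138 = 0.6938
- B = √(0.564 × 0.436 + 0.243 × 0.757) = √(0.24590 + 0.18395) = √0.42986 = 0.6556

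**Step 1: try to reproduce 150**

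- Pooled formula: n = (1.960·A + 1.2816·B)²/d² = (1.3598 + 0.8402)²/0.10304 = 4.8403/0.10304 = 46.97, so **47 per arm**.
- Continuity-corrected: n′ = (n/4)·[1 + √(1 + 4/(n·d))]² = (46.97/4)·(1 + 1.1248)² = 53.02, so **54 per arm**.
- Unpooled: n = (1.960 + 1.2816)²·B²/d² = 10.507 × 0.42986/0.10304 = 43.8, so **44 per arm**.
- Arcsine: 48 per arm.
- Fisher's exact test, by enumeration: power 85.5% at 47 per arm, 90.4% at 52 and 90.7% at 54.
- One-sided alpha 0.05: 39 per arm, or 45 with continuity correction. This is further from 150, so the missing sidedness does not matter.

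None of these is near 150.

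**Step 2: could an unstated adjustment bridge the gap?**

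| Possible explanation | What it gives or needs |
|---|---|
| Dropout of 10% to 20%, n/(1 − dropout) | 53 to 59 per arm from 47; 60 to 68 from 54 |
| Dropout needed to reach 150 | 1 − 54/150 = 64%; 1 − 47/150 = 69% |
| Design effect needed | 150/54 = 2.8; 150/47 = 3.2 |
| Two-sided alpha needed (90% power) | 8.4 × 10⁻⁶ pooled; 1.4 × 10⁻⁵ continuity-corrected |
| 150 meant as the total (75 per arm) | power 98.5%, still not 90% |
| 90% power in each of four equal gestational-age strata | 4 × 47 = 188 per arm, not 150 |

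Of the alpha and power settings tried, only two-sided alpha 0.001 with 99% power and continuity correction came close (147 per arm). That contradicts the stated alpha and power.

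**Step 3: what 150 per arm delivers**

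- Power for 56.4% vs 24.3%: Φ[(d·√150 − 1.960·A)/B] = Φ[(3.9314 − 1.3598)/0.6556] = Φ(3.922) = **99.996%**.
- Detectable difference from a control rate of 56.4%, solving the pooled formula for p2 at n = 150: 90% power for a fall to 37.8%, **18.6 points** (19.2 with continuity correction); 80% power for a fall to 40.3%, 16.1 points.
- If 24.3% is held as the NHFOV rate instead, 90% power corresponds to a control rate of 41.8%, a difference of 17.5 points.

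The stated 32.1 points is 32.1/18.6 = 1.7 times the difference that 150 per arm detects with 90% power.

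**The case against.** The strongest reply is that the error is on the safe side. The trial has at least 90% power for the pilot difference, and the endpoint, test, allocation and type I error are untouched. That is right, and it is why no change in enrolment is asked for. It does not make the derivation correct: 150 is presented as the number the inputs require.

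The investigators may also have had good reasons for more infants. The section concedes that the calculation is difficult and rests on one small study, and planning for a smaller effect than a pilot's is sensible. Four gestational-age subgroups are also prespecified. If the strata were equal (an assumption), 150/4 = 37.5 per arm per stratum would give about 82% power for the pilot difference. Either reason could justify a larger trial, but neither is written down, and the first contradicts the text's statement that the target is the pilot's own difference.

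Two further points stand in part. No rule in the documents judges the result against the design effect; the only stated criterion is a P value below 0.05. The risk that a real effect under 32 points is discounted is therefore one of interpretation, not of the planned decision. And 37.8% appears nowhere in the protocol. It is found by solving for the effect that fits 150, so it can describe what the sample size achieves but must not be presented as the historical rationale unless it was.

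**Conclusion.** The concern holds. The stated rates, alpha, power and sample size are mutually inconsistent by a factor of about three: 47 per arm (pooled) to 54 (continuity-corrected), against 150 stated. Power at 150 per arm for the stated difference is 99.996%, and the difference matched to 90% power is about 18.6 points, not 32.1. These figures assume a two-sided 0.05 test, independent infants, no attrition and, for the detectable difference, a control rate of 56.4%. The conclusion survives a one-sided alpha, every standard variant of the formula, Fisher's exact test and ordinary dropout. The primary comparison is not underpowered for the difference named. What fails is the stated justification for enrolling 300 infants.

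**What to change.** Keep 300 and rewrite the Sample size calculation paragraph.

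1. State the basis on which 150 per arm was actually chosen: a smaller target difference, an attrition allowance, subgroup needs or another reason, with its figures.
2. State that alpha is two-sided (if it is), which formula or test was used, and whether a continuity correction was applied.
3. Replace the claim about the pilot difference with what the sample size delivers, for example:

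> With 150 infants per arm and a two-sided alpha of 0.05, the trial has 90% power to detect a reduction in the need for IMV from 56.4% to about 37.8% (18.6 percentage points), before any allowance for missing outcomes. For the difference seen in the pilot study (56.4% vs 24.3%), power exceeds 99.9%.

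If the investigators had a different target, that target and its power should replace the example. The cost is one paragraph of protocol wording, with no change to enrolment, allocation or analysis.

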(1) Resuscitation requiring early intubation according to the American Academy of Pediatrics guidelines for neonatal resuscitation [8]; (2)major congenital malformations or known complex congenital heart disease; (3)pulmonary hemorrhage or pneumothorax; (4) congenital lung diseases or malformations or pulmonary hypoplasia;

Setting

We plan to enroll preterm infants born between 26 and 34 weeks of gestational age from 18 tertiary NICUs in China. These 18 tertiary NICUs have more than 800 NICU beds and annual admissions of nearly 8,000 preterm infants with RDS each year. The first (XZ) and last authors (RR) take responsibility for the accuracy and completeness

of the trial.

Randomization

To avoid the chance of having more infants in one group than another, block randomization will be applied, with a block size of 4. The envelopes are sealed, shuffled, and then numbered in sequential order from 1 to 4. A clinician who is not in the trial group will open the envelope and randomize patients. This procedure will be repeated for each group of four infants. Infants will be stratified according to 26^{0/7}-27^{6/7} weeks, 28^{0/7}-29^{6/7} weeks, 30^{0/7}-31^{6/7} weeks and 32^{0/7}-33^{6/7} weeks. Infants born from multiple gestations will be assigned by individual randomization. Infants randomized to one arm cannot crossover to the other or vice-versa during the study.

Trial intervention

Ventilators

CPAP: CPAP will be provided by continuous flow devices (CNO Medin, Germany or Carefusion, USA) Bubble CPAP devices will not be used.

NHFOV: NHFOV will be provided by two ventilators (CNO, Medin, Germany or SLE 5000, UK). The Medin CNC ventilator produces high-frequency oscillations by flow interruption with cyclic opening-closure of the end expiratory valve. Otherwise, The SLE 5000 ventilator is a time-cycled, pressure-limited and continuous-flow neonatal ventilator.

Before the beginning of the study all ventilators will be checked to ensure that there is no malfunction.

Interfaces

CPAP and NHFOV will be all administered through short, low-resistance binasal prongs,

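### The primary comparison ignores the gestational-age strata used at randomisation (a small efficiency loss), and the interaction test names a paired model in a trial without pairs.

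*Combined protocol and SAP*

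**What the plan says.** - Randomization uses blocks of 4 and four gestational-age bands, the first given as "Infants will be stratified according to 26^{0/7}-27^{6/7} weeks"; the others are 28-29, 30-31 and 32-33 completed weeks. For siblings, "Infants born from multiple gestations will be assigned by individual randomization". Crossover is ruled out.
- Outcomes makes the primary endpoint binary: need for IMV in the first 7 days of life.
- Statistical methods gives a t-test for continuous data and, for the rest, "compared proportions using Chi-squared test" and Fisher's exact test. Neither stratification nor covariate adjustment is mentioned for the main comparison, and no test is labelled primary.
- The same section uses the four bands again as subgroups: "subgroup analyses will be conducted for the primary outcome in the preterm infants". For heterogeneity, "the test of treatment-by-gestational age subgroup interaction will also be done using the paired binary logistic regression".
- Data collection already records the stratification variable: "Patient demographic data include: sex, birth weight, gestational age".

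**The concern.** There are two separate points.

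**Strata.** Gestational age is the only stratification factor, and the protocol also lets it set oxygen-saturation targets and surfactant thresholds. Balancing the arms within bands removes between-band variation from the true variance of the treatment difference. The plain chi-squared test still charges for that variation, so its standard error is too large if IMV risk differs by band. At stake is some power when the true effect is smaller than planned, and a confidence interval somewhat wider than necessary.

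**Paired model.** A paired (conditional, matched-pair) logistic regression needs pairs. No matching is described, crossover is excluded, and siblings, the only natural pairs, are randomised individually. As written, the model cannot be fitted without inventing pairs afterwards.

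**Working it through.** **1. The plan's own figure.** Sample size calculation uses IMV rates "lower in the NHFOV compared with the NCPAP group (24.3% vs. 56.4"% with "error of 0.05 and a power of 90"%, and states 150 per arm. For a two-sided test without continuity correction,

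n = [1.96 × √(2 × 0.4035 × 0.5965) + 1.2816 × √(0.564 × 0.436 + 0.243 × 0.757)]² / 0.321² = 46.97, so 47 per arm (54 with continuity correction).

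The stated 150 is not reproduced; it gives 99.996% power for that difference. This mismatch is a separate matter, but it explains why no power is at risk at the planned effect.

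**2. Why the plain test is conservative.** Under the null, the within-band share of the binomial variance is R = Σ w p(1-p) / [p̄(1-p̄)], with w the band sizes and p the band risks. The plain test's approximate true level is then P(|Z| > 1.96/√R). The documents give neither w nor p. Assumed: w = 10/25/30/35% from youngest to oldest, and three control-risk gradients, each shifted on the logit scale so that the average is 56.4%.

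| Control IMV risk, youngest to oldest | R | Approximate level, plain test |
|---|---|---|
| Shallow: 70/62/55/50% | 0.983 | 4.8% |
| Moderate: 85/70/55/40% | 0.909 | 4.0% |
| Steep: 90/75/55/35% | 0.853 | 3.4% |

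For example, moderate: (0.10 × 0.85 × 0.15 + 0.25 × 0.70 × 0.30 + 0.30 × 0.55 × 0.45 + 0.35 × 0.40 × 0.60) / (0.565 × 0.435) = 0.2235 / 0.2458 = 0.909.

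**3. Simulation.** 40,000 trials per scenario, 300 infants, permuted blocks of 4 within four strata, Pearson chi-squared against CMH, both without continuity correction.

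| Gradient | Type I error, chi-squared / CMH | Power at OR 0.5, chi-squared / CMH | Change |
|---|---|---|---|
| Shallow | 5.1 / 5.0% | 84.9 / 84.6% | -0.3 |
| Moderate | 4.5 / 5.1% | 79.3 / 80.9% | +1.6 |
| Steep | 3.6 / 4.9% | 74.7 / 78.5% | +3.8 |

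Here OR 0.5 corresponds to average treated risks of 39.6%, 40.9% and 41.9%, that is, differences of 16.8, 15.5 and 14.5 points against the planned 32.1.

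Other stratum sizes at OR 0.5, change with CMH for shallow/moderate/steep:
- equal strata: -0.2/+2.9/+6.3 points
- 5/15/30/50%: -0.6/+0.9/+2.4 points

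A second parameterisation takes 56.4% vs 38%, where power is about 90%, with strata of 10/20/30/40% or equal. The change runs from -0.7 points (no gradient: 90.3% to 89.6%) to +3.2 points (log-odds span of 4 across bands: 94.3% to 97.5%). At that extreme span the plain test's type I error falls to 1.9-2.6%.

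**4. Planned effect.** Power is at least 99.9% with either test. The unstratified Wald 95% interval is 2 × 1.96 × √[(0.564 × 0.436 + 0.243 × 0.757)/150] = 21.0 points wide (20.9 on average in simulation). The Mantel-Haenszel interval averages 20.5, 19.7 and 19.1 points for the three gradients. Judged by the simulated spread of the stratified estimate, the gain is smaller: 20.8, 20.1 and 19.4.

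**5. Interaction test.** An ordinary logistic model with a 3-df likelihood-ratio test (10,000 trials per scenario, moderate and steep gradients) has:
- power of 20.7% and 18.7% if the odds ratio runs 0.25/0.35/0.5/0.7 across bands
- power of 41.8% and 38.0% if it runs 0.2/0.4/0.8/1.0
- a type I error of about 6%, with only about 30 infants (10% of 300) in the youngest band

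This reflects the sample size. Correcting the word *paired* does not change it, but it shows how the result should be labelled.

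**The case against.** The plain test is valid, and against the protocol's own target nothing is lost but a point or two of interval width. The power gain rests entirely on assumed stratum sizes, risks and effect; with a shallow gradient CMH is slightly worse, and +6.3 points needs equal strata, the steepest gradient and an effect under half of that planned. All of this stands, and it is why the point concerns efficiency rather than validity. But the planned effect comes from one pilot study, so a smaller true effect is the case to protect, and there CMH costs at most 0.7 points in the scenarios tried and can gain several.

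If blocks were kept separately at each of the 18 units there would be up to 18 × 4 = 72 cells, about 4 infants each. The documents do not describe blocking by site, and the four bands would remain usable analysis strata in any case.

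*Paired* may be a slip: the outcome, the factors and the purpose are stated, and only the ordinary model makes sense. That is plausible, and the analysis is secondary. The word still names a model that does not fit the design. Correlation between enrolled siblings does not rescue it; that would call for generalised estimating equations or a random effect, not a paired model for every infant.

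**Conclusion.** Both parts hold. The overall comparison of the primary outcome leaves out the one factor on which randomisation is stratified, and the named interaction model does not match a parallel-group trial of individually randomised infants.

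The cost of the first is small: none in power at the planned effect, and a change from about -0.7 to +6.3 points at smaller effects, depending on how steeply IMV risk falls with gestational age and how infants are spread over the bands. Both are assumptions here. The error is in the safe direction, since the plain test rejects too seldom under the null. The second is a specification fault that should be corrected or explained before analysis, because as written it is unclear which model will be run. Together they merit a change, though neither threatens the trial's conclusions.

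**What to change.** In Statistical methods:

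1. Name one primary analysis: a CMH test across the four gestational-age randomisation strata, two-sided at 5%, reported with the Mantel-Haenszel risk difference and 95% confidence interval. Keep the unstratified chi-squared test as a sensitivity analysis.
2. Replace the paired model with ordinary logistic regression containing arm, stratum and arm-by-stratum terms, tested by a 3-df likelihood-ratio test. Label it exploratory, and state its low power and its slightly raised error rate with a small youngest band. If pairing was really intended, define the pairs.
3. Because missing outcomes are to be multiply imputed, say how results are combined. Pooling the Mantel-Haenszel risk difference over imputations is routine; the method for the interaction test should be named as well.

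The cost is revised wording and a few lines of code. Gestational age is already collected, so no new data are needed, and the sample size does not change.

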Caffeine (Caffeine Citrate Injection, Chiesi Pharmaceuticals, Parma, Italy) will be administered when infants present with moderate apnea (defined as 3 or more episodes in 24 hours or a single episode requiring resuscitation and bag-mask ventilation). The initial loading dose is 20mg/kg, and the maintenance dose is 5mg/kg per day.

Weaning from study interventions

The criteria for weaning noninvasive respiratory will be: (1) minimal or no signs of respiratory distress (RDS Silverman score < 5) ; (2) NHFOV MAP or NCPAP pressure <6 cmH₂O and (3) $FiO_2 < 0.25$ to achieve target SpO₂.

Criteria for intubation and IMV

These will be as follows [10-11]: (1)severe respiratory acidosis ($P_aCO_2 > 65$ mmHg with $pH < 7.20$);(2)severe apnea and bradycardia (defined as recurrent apnea with >3 episodes per hour associated with heart rate < 100 /min, a single episode of apnea that

requires bag and mask ventilation); (3) hypoxia ($FiO_2 > 0.5$ with $PaO_2 < 50$ mmHg), severe respiratory distress (RDS Silverman score > 7); (4) pulmonary hemorrhage; (5) pneumothorax; (6) cardiopulmonary arrest needing chest compressions.

Training

Since not all clinicians are well versed in all respiratory techniques and, particularly, NHFOV is a relatively new technique, the training is capital for the trial success. The protocol will be diffused between participating centers at least 3 months before the study begins. One investigator (YS) will explain the study protocol in an in-person meeting with all investigators. During the two months' period, clinicians will familiarize with the protocol and the respiratory techniques and the two co-principal investigators will be available to solve any doubt. A dedicated social media chat has been set to facilitate these exchanges. The trial is supposed to actually start in July 2017.

Outcomes

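### Adjusting the primary comparison of IMV for baseline values already collected would narrow the confidence interval at almost no cost; the crude test is valid, and the size of the gain rests on assumptions

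*Combined protocol and SAP*

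**What the plan says.** The Outcomes section defines the primary outcome as the "need for IMV in the first 7 days of life in preterm infants randomized to the two groups", which is binary. Statistical methods names no test for it separately. For group comparisons it lists Student's t-test, "compared proportions using Chi-squared test" and Fisher's exact test, so the primary comparison is crude. The one model that uses a baseline value is a logistic regression for the interaction of arm with gestational-age band. That is a subgroup analysis.

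Under Data collection, the values recorded for each infant include "sex, birth weight, gestational age, Apgar scores" and "prenatal corticosteroid use, premature rupture of the membrane, RDS Silverman score and critical risk index for babies-II (CRIB-II) score". None of these is given a role in the primary analysis. Appendix A3 describes CRIB-II as a measure of severity at admission, built from birth weight, gestational age, base excess and temperature.

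The Silverman score appears in two other places. Inclusion criterion 3 requires a score above 5, and Criteria for intubation and IMV lists "severe respiratory distress (RDS Silverman score > 7"). Randomization is stratified by four gestational-age bands and by nothing else.

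The Sample size calculation takes 24.3% vs 56.4% from one pilot study, with alpha 0.05 and power 90%, and concludes that "150 neonates should be enrolled in each arm (with a 1:1 design").

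**The concern.** When baseline values predict a binary outcome, a prespecified adjusted analysis estimates the same difference in risk with a smaller standard error. This trial records several plausible predictors of IMV, and the Silverman score shares a scale with one of the intubation criteria. Leaving them all out makes the interval wider than it need be.

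This matters most if NHFOV works less well than in the pilot. The planned effect rests on a single preliminary study, and the Sample size calculation itself says that the number is hard to derive. Covariates can be chosen credibly only in advance, because adjustment added after the results are known would look data-driven.

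**Working it through.** **Inputs from the protocol.** Control rate 56.4%, NHFOV rate 24.3%, 150 per arm, alpha 0.05 (taken as two-sided; the protocol does not say), power 90%.

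**Inputs assumed.** Covariate strengths, since the documents give none, and a smaller effect of 39.5% vs 55%, which is not in the protocol.

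**1. The plan's own figure.** The usual formula is n = [1.96·√(2p̄(1−p̄)) + 1.2816·√(p₁(1−p₁)+p₂(1−p₂))]² / (p₁−p₂)². With p̄ = 0.4035:
- n = (1.96 × 0.6938 + 1.2816 × 0.6556)² / 0.321² = 4.840 / 0.1030 = 47 per arm.
- The stated 150 does not reproduce. That is a separate matter; here it means that the trial has ample power for the planned effect.

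**2. Crude power at the planned effect, 150 per arm.** Null SE = 0.6938/√150 = 0.0567; alternative SE = 0.6556/√150 = 0.0535.
- Power = Φ[(0.321 − 1.96 × 0.0567)/0.0535] = Φ(3.92), above 99.9%.
- Adjustment cannot usefully raise this.

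**3. How far the variance falls.** Simulated trials of 300 infants compared the crude difference with the standardised risk difference from logistic regression, using two independent standardised severity covariates. Separate runs gave these ratios of crude to adjusted variance:

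| Odds ratios per SD (assumed) | Variance ratio |
|---|---|
| 1.5 and 1.35 | 1.02 to 1.05 |
| 1.8 and 1.65 | 1.13 to 1.14 |
| 2.5 and 2.0 | 1.24 to 1.25 |

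A ratio r means a variance reduction of 1 − 1/r: 2% at 1.02 and 20% at 1.25. Effective sample size rises by about 2% to 25%. Type I error was about 5-6% for both analyses. A check with a single prognostic index, c-statistic 0.58 to 0.80 (assumed), gave reductions of 1.5% to 26%.

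**4. Interval width.** Half-width = 1.96·√[(p₁(1−p₁)+p₂(1−p₂))/150], divided by √r after adjustment.
- Planned rates: 1.96 × √(0.4299/150) = 10.5 points, becoming 10.4 (r = 1.02) to 9.4 (r = 1.25).
- 39.5% vs 55%: 1.96 × √(0.4865/150) = 11.2 points, becoming 11.1 to 10.0.

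**5. Power at 39.5% vs 55%.** Simulated crude power is about 79%, and adjustment adds about 2 to 7 points. The normal approximation gives Φ[(0.155 − 1.96 × 0.0577)/0.0569] = 77% crude. Dividing both SEs by √r gives 78% at r = 1.02 and 86% at r = 1.25, a rise of about 1 to 8 points, which agrees. With 2,000 runs, the Monte Carlo SE of a simulated power near 79% is √(0.79 × 0.21/2000), or 0.9 point.

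**6. Silverman score alone.** With an assumed five-point score (6 to 10, skewed low) as the only prognostic covariate, the variance ratio was 1.05 at an odds ratio of 1.8 per SD and 1.16 at 2.5. If infants mostly entered at 6 or 7 (assumed), the SD would be at most 0.5, and those odds ratios would mean 1.8² = 3.2 and 2.5² = 6.3 per point, which is demanding.

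**The case against.** The strongest reply is that nothing is wrong. A crude chi-squared test is valid in a randomised trial, power at the planned effect is near certain, and the gain rests wholly on assumed covariate strengths, with a low end of about 2%. All of this stands. It limits the point to precision but does not remove it: in the simulations adjustment carried no type I error penalty, and the data are already being collected.

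A reader might infer more than the documents support:

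- **That chance imbalance biases the crude result.** If 30% entered with a Silverman score above 7 (assumed), chance alone could produce an imbalance of up to about 1.96·√(2 × 0.3 × 0.7/150), or 10 points. The crude P-value already allows for such chance differences; adjustment only reduces the noise.
- **That the Silverman score matters above all.** This is inferred from its place among the intubation criteria. Entry above 5 truncates its range, and the documents do not say how infants already above 7 at entry are handled. Gestational age and CRIB-II are equally natural candidates.
- **That crude power falls as covariates become stronger.** It does not at fixed arm rates. Holding a conditional odds ratio near 0.48 fixed instead moves the NHFOV rate from 37.9% to 40.6%, against 55%, and crude power from 86% to 72%, because the true effect itself shrinks.
- **That the lack of a stated effect estimate argues for adjustment.** A crude risk difference with a confidence interval would fill that gap, so it is a separate point.

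**Conclusion.** The point holds as a low-cost improvement in precision. It does not correct an error. Under the assumed strengths the variance of the risk difference falls by roughly 2% to 20%. At the planned rates that takes the 95% half-width from 10.5 points to between 10.4 and 9.4. If the effect is nearer 39.5% vs 55%, power rises by about 2 to 7 points from about 79%.

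These figures assume two independent covariates. The real ones overlap, since birth weight and gestational age are related and CRIB-II contains both, so the upper end should not be counted on. The documents support neither a claim that the trial is underpowered for its planned effect nor a claim that its primary test is invalid.

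**What to change.** In Statistical methods, before outcome data are seen, make the primary analysis a logistic regression of IMV on:

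- arm;
- gestational age (the four randomisation bands, or continuous; state which);
- the Silverman score at entry, recorded before randomisation (state its form);
- birth weight, or CRIB-II in its place, as it already contains birth weight and gestational age;
- prenatal steroids.

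Report the standardised (marginal) risk difference with 95% CI and P-value, pooled over the planned multiple imputations. Do not let the adjusted odds ratio replace it, because that is a different quantity from the crude contrast. Keep the crude chi-squared test as a supportive analysis.

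The cost is a short paragraph and a little extra programming, possibly outside the SPSS 19 menus. No new data or infants are needed. If the covariates prove weak, the gain will be negligible.
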